**Measures:**

Demographic characteristics and health information. Information on mom and baby with regards to race/ethnicity, age, education, income, marital status, parity, substance use,

general health, health behaviors, health care utilization will be ascertained from a combination of KPNC EHR databases and the online surveys.

### **Outcomes**

**Physical Activity.** PA will be measured using accelerometry (Actigraph wGT3X-BT physical activity monitor) and self-report (sports/exercise domain of the Pregnancy Physical Activity Questionnaire) at T0, T1, and T2.

**Depression and Depressive symptoms.** Depressive symptoms will be measured at recruitment, T1, and T2 using the Patient Health Questionnaire (PHQ-8) and assessed as a continuous outcome. The 8-item, PHQ-8 depression screener is a validated instrument adapted from the PHQ-9. The PHQ-8 excludes the question regarding suicidal thoughts. PHQ-8 scores range from 0-24. A score of 1-4 suggests minimal depression, 5-9 mild depression, 10-14 moderate depression, 15-19 moderately severe depression and 20-24 severe depression. Depression diagnoses will be ascertained from the EHR.

**Anxiety and Anxiety symptoms.** Anxiety symptoms will be evaluated using the Generalized Anxiety Disorder 7-Item Scale (GAD-7), a self-rated assessment developed to screen for general anxiety disorder. Anxiety diagnoses will be ascertained from the EHR.

**Adherence.** The MomZing website automatically records adherence data (time, type, date, duration of exercise video) for each participant. Quarterly usage reports for participants in the intervention will be generated and sent to us by Klein Buendel.

**Additional outcomes measures included in the survey:** sleep, patient satisfaction, self-efficacy, social support for and barriers to PA, the impact of COVID-19 on pregnancy, substance use measures, and infant development.

**Implementation evaluation measures.** Process measures and key stakeholder interviews will be used to assess the Reach, Effectiveness, Adoption, Implementation, and Maintenance components of the RE-AIM framework. *Reach* of the intervention will be evaluated using the participation rate among contacted eligible participants and comparison of characteristics available in the EHR between participants and eligible non-participants. *Effectiveness* will be measured through the results of the randomized controlled trial, by examining the data for a dose-response association between intervention engagement/adherence (number of exercise videos viewed), PA, and depressive symptoms, and through participant satisfaction with the intervention. Satisfaction will be assessed as part of the T1 online surveys. *Adoption* will be assessed by calculating personnel costs associated with the intervention (e.g. clinic referral staff). Additionally, key stakeholder interviews with clinicians and clinical leaders will address identified avenues for *adoption* of MomZing and barriers to *implementation* and *maintenance* within clinical practice at KPNC. The standard criteria for generating a RE-AIM public health impact score will be followed.

- The duration of an individual subject's participation in the study.

For the patient participants, participation will begin between 2 and 6 months postpartum (baseline), depending when they are recruited, and will conclude after the women complete the final survey when their child is 12 months old.

For the clinicians, participation is complete after the one-time interview to identify barriers and addressing implementation and evaluate potential adoption of MomZing.

- The duration anticipated to enroll all study subjects.

The anticipated duration to enroll all study subjects will be from 08/01/2020-03/31/2022.

		Year 1		Year 2		Year 3	
IRB approval		M					
MomZing development/final product		D					D
Clinic implementation workflow/protocol		D					D
Participant recruitment						M	
Data collection							M
Stakeholder interviews		M					M
Data analysis							M
MomZing effectiveness manuscript							D
Implementation findings report							D

M=milestone, D=deliverable

- The estimated date for the investigators to complete this study (complete primary analyses)  
 NOTE: It should be clear exactly which procedures will be conducted for the research as opposed to procedures the subjects would undergo (in the exact manner described in the protocol) even if they were not participating in the study.

The estimated date will be 12/31/2022.

- Describe procedures that will be followed when subjects withdraw from the research, including withdrawal from intervention but continued information and/or biospecimen collection.

During recruitment, participants will be informed that their participation in the study is completely voluntary and that they are free to refuse to participate in the study. Their decision whether or not to participate in the study will not affect their medical care. If they decide to participate, they are free to change their mind and discontinue participation at any time without any effect on their medical care or eligibility for future care or membership in KFHP. At any time during the study, if participants no longer want to participate or have their information used as part of the study, they must write a letter stating that they withdraw their participation and authorization and send it to the PI, [name], at which time we would remove her from the study. We will use any PHI obtained for this study before they withdraw their authorization but will not use any PHI obtained after their withdrawal.

- Describe any anticipated circumstances under which subjects could be withdrawn from the research without their consent.

Women who become pregnant during the study will be withdrawn from the study.

- Describe any procedures for orderly termination.

N/A

- If the study involves genetic testing or collection of genetic information, describe this.

N/A

- Clarify whether research involving biospecimens will (if known) or might include whole genome sequencing (i.e., sequencing of a human germline or somatic specimen with the intent to generate the genome or exome sequence of that specimen).

N/A

b. Data Analysis

Describe the data analysis plan, including:

- Statistical procedures.

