**2. Objectives**

Describe in plain language the purpose, specific aims, or objectives and indicate the primary goal(s) of the study (e.g. safety, tolerability, effectiveness, feasibility, pilot study, etc.). State the hypotheses to be tested. State primary and any secondary study endpoints.

The purpose of this study is to address a high priority area of the KP-NBA Exercise as Medicine initiative and the critical need for evidence-based interventions for increasing physical activity (PA) and preventing postpartum depression (PPD) that do not involve intense health care system resources through the aims below. This study will also identify actionable avenues for implementation of this eHealth PA intervention at KPNC and potentially other KP regions in the future.

Aim 1. Conduct an effectiveness trial of MomZing, an eHealth PA intervention, in women at increased risk of postpartum depression (PPD) for a) increasing PA and b) decreasing depressive symptoms.

Aim 2. Evaluate procedures for implementation of MomZing at KPNC. We will use the RE-AIM framework (Reach, Effectiveness, Adoption, Implementation, Maintenance) to evaluate procedures for implementation of MomZing including documentation of web access to MomZing exercise videos (website analytics), process measures (participant satisfaction with the

intervention), and qualitative interviews with KPNC clinical staff (barriers to adoption/maintenance).

**Exploratory Aim 1:** Assess the impact of MomZing on improving maternal outcomes (e.g. postpartum depression diagnoses, anxiety, stress, sleep, medical conditions, substance use, health care utilization) and infant outcomes (e.g. growth and development, health care utilization). Describe maternal and infant characteristics associated with greater levels of engagement/use of the MomZing intervention.

**Exploratory Aim 2:** Identify mediators and moderators (e.g. previous physical activity, maternal infant bonding, perceived barriers to physical activity, social support) in the relationship between MomZing and maternal and infant outcomes (as listed above).

**Exploratory Aim 3:** Assess relationships between exercise and other health behaviors (e.g. sleep, sitting, substance use, smoking) and maternal and infant outcomes.

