Strong evidence suggests postpartum PA is effective in preventing PPD; however, several barriers to PA keep postpartum women from being physically active. The PA Guidelines for Americans, the American College of Sports Medicine, and the American College of Obstetricians and Gynecologists recommend participation in regular PA (at least 150 minutes of moderate to vigorous intensity per week) for postpartum women. Despite these recommendations, PA levels in postpartum women remain low: only one third of postpartum women report being regularly physically active in the year after delivery. Low postpartum rates of PA contribute to postpartum weight retention, overweight, and obesity. We conducted focus groups among KPNC members with PPD and found similar barriers to PA during the postpartum period as has been reported by others: lack of time and prioritization of other responsibilities, difficulty finding accessible and affordable PA programs and classes, lack of child care, and lack of motivation and social support. Most previous PA interventions in

postpartum women have relied on in-person exercise groups alone or in combination with individual in-person or telephone-based health coaching. These approaches do not address the barriers to being physically active identified in postpartum women.

Technology-based (eHealth) interventions are a promising approach to increasing PA levels that address barriers raised by postpartum women. New mothers are frequent users of technology and welcome eHealth interventions. eHealth PA interventions have demonstrated effectiveness in increasing PA in general populations. In addition, MomZing, an eHealth intervention tailored to postpartum women, was effective in increasing the proportion of postpartum women meeting national PA guidelines. MomZing was developed by exercise physiologists and behavioral medicine specialists and addresses accessibility, affordability, time constraints, and child care concerns.

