Describe whether the research involves benign behavioral interventions on **adult** subjects. Note: Benign behavioral interventions are brief in duration, harmless, painless, not physically invasive, not likely to have a significant adverse lasting impact on the subjects, and not offensive or embarrassing to the subjects. Examples include having subjects play online games or solving puzzles under various noise conditions.

As described above, all eligible women will be asked to wear a research-grade accelerometer for 7 days to assess baseline PA and then randomized into MomZing (intervention) or Usual care (control). They will wear the accelerometer again for 7 days at 3 months post-baseline and 6 months post-baseline.

MomZing intervention: the MomZing online exercise application ([www.momzing.com](http://www.momzing.com)) was developed based on mothers' preferences for exercise videos that: 1) instructed mothers how to

exercise safely with their baby based on the infant's weight and developmental stage; 2) did not require exercise equipment or a substantial time commitment per video (e.g., maximum time per video 10 minutes); 3) provided different types of physical activities (e.g., yoga, strengthening, cardio) and intensity levels (light, moderate, hard); and finally, 4) featured women in the exercise demonstrations who were "real" mothers (not fitness instructors) exercising with their own infant. Users can either select up to three 10-minute videos to create a 10 to 30-minute workout or choose a 'Ready Made' workout that is either 10, 20, or 30-minutes long.

If the study involves either educational tests, survey procedures, interview procedures, or benign behavioral interventions (on adults), specify whether one of the following criteria is met:

(i) The information obtained is recorded by the investigator in such a manner that the identity of the human subjects cannot readily be ascertained, directly or through identifiers linked to the subjects

N/A

(ii) Any disclosure of the human subjects' responses outside the research would not reasonably place the subjects at risk of criminal or civil liability or be damaging to the subjects' financial standing, employability, educational advancement, or reputation

N/A

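### A dose-response with videos viewed is counted as effectiveness evidence, although viewing is self-selected after randomization and could track outcome without any intervention effect

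*Combined protocol and SAP*

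**What the plan says.** Under Implementation evaluation measures in Section 9.a, RE-AIM Effectiveness "will be measured through the results of the randomized controlled trial", then "by examining the data for a dose-response association between intervention engagement/adherence (number of exercise videos viewed), PA, and depressive symptoms", and also through participant satisfaction. The three routes stand side by side in one sentence, and none is marked as secondary, exploratory or non-causal.

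The exposure comes from the site's own logs. Section 9.a, Adherence: "The MomZing website automatically records adherence data (time, type, date, duration of exercise video) for each participant". The same paragraph limits the reports to one arm: "Quarterly usage reports for participants in the intervention will be generated". The amount of use is left to the participant. Section 4: "Users can either select up to three 10-minute videos to create a 10 to 30-minute workout", with a ready-made workout as the alternative. No assigned number of videos is stated.

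Two other places bear on who will use the site more. Section 3.a lists among the barriers to activity "lack of child care, and lack of motivation and social support". Exploratory Aim 1 in Section 2 undertakes to "Describe maternal and infant characteristics associated with greater levels of engagement/use of the MomZing intervention".

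Section 9.b (Statistical Analysis) sets out GEE models with study arm and time, adjusted for the randomization covariates, baseline depression score and household income. It gives no model, population, exposure window or adjustment set for the dose-response.

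**The concern.** Number of videos viewed is behaviour that occurs after randomization, so the comparison of heavy and light users inside the MomZing arm has no protection from the allocation. A woman whose mood is lifting, who has more time, or who is more motivated may watch more and also be more active and less depressed. PHQ-8 is taken at recruitment, 3 months and 6 months while viewing accrues, so mood can influence viewing as well as the reverse.

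The text as written lets this association count towards an effectiveness conclusion on the same footing as the randomized result. That matters most if the arm comparison turns out null or borderline, because the plan then contains a second, non-randomized measure under the same label and no sentence limiting how it may be read.

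**Working it through.** **Inputs from the documents.** 100 women per arm, two-sided alpha .05, up to 16% loss to follow-up, a detectable difference of .43 SD for depressive symptoms, and power .80 for 43% versus 23% meeting activity guidelines (all Section 9.b, power analysis). Analysed number in the MomZing arm: 100 × (1 − 0.16) = 84.

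**The plan's own figures.** Detectable difference = (1.960 + 0.842) × √(2/84) = 0.432 SD, against .43 stated. Power for 43% versus 23% at 84 per arm is 0.793, against .80 stated. Both reproduce, so 84 is the number the plan itself implies. The point below does not depend on these figures being right or wrong.

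**What the plan would need, and what it has.** To read a within-arm association as an effect of viewing, all common causes of viewing and outcome must be measured and adjusted for, and viewing must precede the outcome.
- Section 9.b states its covariates for models that contain study arm and time, and says nothing about a within-arm dose model.
- Those covariates include baseline depression score but no measure of motivation or available time. Self-efficacy, social support and barriers are surveyed (Section 9.a) but assigned to no such model.
- No viewing window is defined relative to the 3- or 6-month assessment.

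**Illustration 1: total correlation.** Suppose MomZing has no effect and confounding alone gives a correlation ρ between viewing and outcome. The values of ρ are assumptions; the documents give none. Fisher z approximation: power ≈ Φ(√(84 − 3) × atanh(ρ) − 1.96) + Φ(−√(84 − 3) × atanh(ρ) − 1.96), with √81 = 9. The last column is the correlation a single hidden factor would need with viewing and with outcome, √ρ, because the two paths multiply.

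| ρ assumed | 9 × atanh(ρ) | Chance of p < .05 | Hidden-factor correlation needed, √ρ |
|---|---|---|---|
| 0.1 | 0.903 | .147 | 0.32 |
| 0.2 | 1.825 | .446 | 0.45 |
| 0.3 | 2.786 | .796 | 0.55 |

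**Illustration 2: with baseline adjustment.** Simulation with 84 per arm, 4000 runs, and no effect of arm or of videos. Baseline score correlates 0.5 with 3-month PHQ-8. A hidden factor, independent of baseline, correlates r with viewing and −r with 3-month PHQ-8. The regression adjusts for baseline PHQ-8.

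| r assumed | Mean slope (SD of PHQ-8 per SD of viewing) | Dose-response p < .05 | Arm comparison p < .05 |
|---|---|---|---|
| 0.2 | −0.04 | 7.2% | 5.4% |
| 0.3 | −0.09 | 14.8% | 5.4% |
| 0.4 | −0.16 | 38.2% | 5.5% |
| 0.5 | −0.25 | 75.2% | 4.9% |

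The two illustrations agree once r is read correctly. In the second, the induced slope is r² in size, and the partial correlation given baseline is r²/√(1 − 0.25). At r = 0.3 that is 0.09/0.866 = 0.10, which matches the first row of the first table. At r = 0.5 it is 0.25/0.866 = 0.29, close to the last row. Baseline adjustment removes only the confounding that runs through the baseline score. The arm comparison stays near 5% throughout.

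**The case against.** The strongest reply is that this is peripheral. The sentence belongs to Aim 2, the implementation evaluation. Effectiveness is tested under Aim 1 by the arm-based GEE models of Section 9.b, the randomized result is named first in the disputed sentence, and the effectiveness manuscript and the implementation report are separate deliverables. All of that is correct. A reader might infer that the dose-response could replace or override a null trial; nothing in the documents says so.

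The second reply is that the plan speaks only of examining the data, with no model or test, so there is no stated method to call wrong. That is partly right: much of the defect is missing specification. But the role given to the result is stated, and that role is what needs correcting.

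Third, a reader might infer that the analysis is bound to show a dose-response, or that it is biased in favour of MomZing. The documents support neither. Women with persistent symptoms might use the site more, and women who recover might stop, which would push the association the other way.

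Fourth, the percentages restate assumed correlations, and a total correlation of 0.3 sounds modest but requires a hidden factor correlated about 0.55 with both variables. That is why both scales are shown. None of these replies supplies a reason to treat self-selected viewing as a measure of effectiveness.

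**Conclusion.** The concern holds in a limited form. The plan counts a within-arm, self-selected association as one of three measures of RE-AIM Effectiveness, and no passage qualifies it. Such an association could arise from mood, time or motivation with no intervention effect, in either direction, and baseline PHQ-8 adjustment does not cure it.

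Its size cannot be fixed from the documents. On assumed values it runs from little above the nominal 5% (7.2% for a hidden factor at 0.2 on each path) to 75% or more for strong confounding (0.5 or higher). These figures also assume 84 women analysed, a linear relation and a single test; with baseline adjustment, they assume a factor independent of the baseline score.

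The primary GEE comparison by arm and the sample size are untouched. What is at stake is the wording of the Aim 2 effectiveness conclusion. It is worth correcting before the analysis begins.

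**What to change.** In Section 9.a, Implementation evaluation measures:
- State that the conclusion on Effectiveness rests on the randomized comparison.
- Move videos viewed against activity and depressive symptoms to Implementation, labelled as an exploratory, non-causal description of use.
- Specify it: intervention women only, adjusted for the Section 9.b covariates, using viewing logged before the outcome assessment (for accelerometry, before the wear week). The logs hold dates, so this is feasible. It settles the time order but does not remove confounding, so the label stays.

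Optionally, if a causal effect of use is wanted, add a complier-average estimate with randomized arm as instrument for any use. The exclusion assumption must be stated, since the intervention also includes goal setting and workout tracking, and participants are unblinded and self-report PHQ-8. The plan should say that this estimate rescales the randomized effect, is not independent evidence and does not describe a dose-response.

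The cost is a wording change and minor analysis work on data already collected. The trial gives up one favourable-looking line of effectiveness evidence. The optional estimate adds modelling for two outcomes at two follow-up times.
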